1.2 SCHEMA

Figure 1 - Graphical study design

★ Treatment consisting of 2 injections of 1.5 mL each of SAR440340 or placebo.

¹ Variable treatment period determined by either completion of a 52 week treatment duration or the end of treatment of the last patient completing planned treatment (EOT visit), whichever occurs earlier, whichever occurs earlier [Section 4.1](#).

² End of Treatment (EOT) visit to occur 2 weeks after last administration of IMP.

1.3 SCHEDULE OF ACTIVITIES (SOA)

The Schedule of Activities (SoA) for patients who complete the planned treatment is described in Section 1.3.1. Patients who withdraw treatment must complete the Early Treatment Discontinuation (ETD) visit and follow the assessment in Section 1.3.2 for the remaining visits.

1.3.1 Schedule of Activities (SoA) for Patients who complete the Planned Treatment

	S	R/ B																																					
VISIT	1	2 ^{a, b}	3	4	5	6	7	8	9	10	11	12	13	14	15	16	17	18	19	20	21	22	23	24	25	26	27	EOT ^c	F1	F2 ^d	EOS								
WEEK	W-4 to W-1	0	2	4	6	8	10	12	14	16	18	20	22	24	26	28	30	32	34	36	38	40	42	44	46	48	50	52	60	66	72								
Informed consent	X																																						
Patient demography	X																																						
Previous medical and surgical history	X																																						
Chest X-ray ^e	X																																						
Inclusion/exclusion	X	X																																					
COPD Assessment Test (CAT) ^f	X	X																																					
Smoking status	X	X	X	X	X	X	X	X	X	X	X	X	X	X	X	X	X	X	X	X	X	X	X	X	X	X	X	X	X	X	X	X	X	X	X	X	X	X	
Prior & concomitant medications	X	X	X	X	X	X	X	X	X	X	X	X	X	X	X	X	X	X	X	X	X	X	X	X	X	X	X	X	X	X	X	X	X	X	X	X	X	X	
Study treatment administration																																							
Call IVRS/IWRS	X	X	X	X	X	X	X	X	X	X	X	X	X	X	X	X	X	X	X	X	X	X	X	X	X	X	X	X	X	X	X	X	X	X	X	X	X	X	
Randomization		X																																					
IMP administration ^g		X	X	X	X	X	X	X	X	X	X	X	X	X	X	X	X	X	X	X	X	X	X	X	X	X	X	X	X	X	X	X	X	X	X	X	X	X	
Dispense or upload electronic diary ^h	X	X	X	X	X	X	X	X	X	X	X	X	X	X	X	X	X	X	X	X	X	X	X	X	X	X	X	X	X	X	X	X	X	X	X	X	X	X	X
Safety																																							
Physical examination ⁱ	X	X						X						X														X									X		
Vital signs ^j	X	X	X	X	X	X	X	X	X	X	X	X	X	X	X	X	X	X	X	X	X	X	X	X	X	X	X	X	X	X	X	X	X	X	X	X	X	X	
Electrocardiogram (12 lead) ^k	X	X						X						X														X									X		
Hematology, biochemistry, urinalysis including	X	X				X				X				X														X									X		

	S	R/ B																																									
VISIT	1	2 ^a , b	3	4	5	6	7	8	9	10	11	12	13	14	15	16	17	18	19	20	21	22	23	24	25	26	27	EOT ^c	F1	F2 ^d	EOS												
WEEK	W-4 to W-1	0	2	4	6	8	10	12	14	16	18	20	22	24	26	28	30	32	34	36	38	40	42	44	46	48	50	52	60	66	72												
cotinine ^l																																											
Hepatitis and HIV Serology tests ^m	X																																										
Quantiferon Gold	X																																										
Pregnancy (β-HCG blood) test ⁿ	X																																										
Urine pregnancy test ⁿ		X		X		X		X		X		X		X		X		X		X		X		X		X		X									X						
Adverse event reporting, including SAEs	X	X	X	X	X	X	X	X	X	X	X	X	X	X	X	X	X	X	X	X	X	X	X	X	X	X	X	X	X	X	X	X	X	X	X	X	X	X					
Pharmacokinetics																																											
Serum samples for SAR440340 concentration ^o		X	X	X		X		X		X				X																							X	X		X			
Anti-SAR440340 antibody ^p		X						X						X																								X			X		
Biomarkers																																											
Blood eosinophils and neutrophils	X	X		X ^q		X		X ^q						X																							X	X ^q		X			
Total IL33 and sST2 ^o	X	X		X		X		X						X																								X	X		X		
Calcitonin	X	X		X		X		X						X																								X	X		X		
PARC	X	X		X				X						X																								X					
Eotaxin-3	X	X		X				X						X																								X					
Total IgE	X	X		X				X						X																								X					
Fibrinogen	X	X												X																							X						
FeNO pre-bronchodilator (optional) ^f		X		X		X		X						X																													
FeNO post-bronchodilator (optional) ^f		X		X		X		X						X																													
Induced sputum (optional) ^s		X												X																									X				
Blood samples for RNA sample (optional)	X	X		X										X																									X				
Blood sample archival for exploratory research (optional) ^t	X	X		X				X						X																										X			

	S	R/ B																																		
VISIT	1	2 ^{a, b}	3	4	5	6	7	8	9	10	11	12	13	14	15	16	17	18	19	20	21	22	23	24	25	26	27	EOT ^c	F1	F2 ^d	EOS					
WEEK	W-4 to W-1	0	2	4	6	8	10	12	14	16	18	20	22	24	26	28	30	32	34	36	38	40	42	44	46	48	50	52	60	66	72					
DNA Pharmacogenomics analysis (optional)		X																																		
Efficacy																																				
COPD exacerbation reporting by the Investigator		X	X	X	X	X	X	X	X	X	X	X	X	X	X	X	X	X	X	X	X	X	X	X	X	X	X	X	X	X	X	X	X	X		
Spirometry (pre-BD) ^{u, v}	X	X	X	X		X		X		X		X		X		X		X		X		X		X		X		X		X		X		X		
Spirometry (post-BD) ^{u, v}	X	X	X	X		X		X					X							X								X				X		X		
EXACT ^w	Every day (diary) from screening to week 52																																			
SGRQ ^w		X		X		X		X						X						X								X		X		X		X		
EQ-5D-5L ^w		X												X														X		X		X		X		
Actigraphy Optional assessments (US/Canada only)	Co n- tin uous							Con- tinuos						Con- tinuos																						
At-home spirometry (FEV1) Optional assessments (US/Canada only)	BI D							BID						BID																						

S= Screening; R/B= Randomization/Baseline; F=Follow-up
β-hCG = Human chorionic gonadotropin-beta; BID = twice daily assessments; CAT = COPD Assessment Test; continuous = subsequent visits during the treatment period; COPD = chronic obstructive pulmonary disease; cont. = continuous; DNA = Deoxyribonucleic acid ; EDTA = Ethylenediaminetetraacetic acid ; EOS = End of Study; EOT = End of treatment; EQ-5D= Euro Quality of Life-5 Dimension questionnaire; EXACT = Exacerbations of COPD tool (EXACT); HIV = human immunodeficiency virus; IgE = Immunoglobulin E; IMP = Investigational Medical Product; IVRS = Interactive Voice Response System; IWRS = Interactive Web Response System; LABA = Long-acting β2 adrenergic agonist; LAMA = Long-acting muscarinic antagonist ;PARC = Pulmonary and activation-regulated chemokine; PK = Pharmacokinetic; RNA = Ribonucleic acid; SABA = Short-acting beta-agonists; SAEs = Serious adverse events; SC = subcutaneous; SGRQ = St. George's Respiratory Questionnaire.

a Randomization/baseline Visit is defined as Day 1. The visit schedule should be adhered to within ±3 days for the screening period and randomized IMP treatment period, and ±5 days for the 2 visits during the post IMP treatment period.

b All assessments at Visit 2 (Day 1) are to be conducted pre-IMP dose with the exception of the assessment of local tolerability of SC injections.

c End-of-treatment visit: See Section 4.1 for patients who discontinue treatment.

d Can be performed with a phone call.

e Chest X-ray to be performed unless a <6 month old chest x-ray/chest CT/chest MRI is available. In case chest-X-ray is not feasible due to local regulations, magnetic resonance imaging (MRI) will be performed.

f The COPD Assessment Test (CAT) is to be registered through the patient's electronic diary.

g IMP (SAR440340 or placebo) to be administered every 2 weeks at the site. Last dose will be given 2 weeks prior to planned EOT visit eg, for patients with 52-week treatment period the last dose will be taken at Week 50, or earlier, as directed by the sponsor. Patients should be monitored by site personnel for at least 30 minutes after administration of all IMP injections. Monitoring period may be extended as per country specific requirements.

- h* Electronic diary is used for recording of patient's answers to the EXACT, SGRQ and EQ-5D-5L questionnaires, CAT assessment as well as for recording reliever medication. This device is dispensed at Screening Visit 1 (including instructions for use) and recorded information is downloaded from this device on the other indicated days. At EOS visit the electronic diary is downloaded and returned to the site.
- i* Complete physical examinations will include skin, nasal cavities, eyes, ears, respiratory, cardiovascular, gastrointestinal, neurological, lymphatic, and musculoskeletal systems.
- j* Vital signs, including systolic and diastolic blood pressure (mmHg), pulse rate (beats per minute), body temperature (°C), and respiratory rate will be measured at screening, baseline and every subsequent on-site visit. Height (cm) will be measured at screening (Visit 1) only. Body weight (kg) will be measured at screening (Visit 1) and at EOT/EOS visits.
- k* ECG to be centrally collected & read.
- l* Hematology will include hemoglobin, hematocrit, platelet count, total white blood cell count with 5-part differential count, and total red blood cell count. Serum chemistry will include creatinine, blood urea nitrogen, glucose, lactate dehydrogenase, uric acid, total cholesterol, total protein, albumin, total bilirubin, alanine aminotransferase, aspartate aminotransferase, alkaline phosphatase, electrolytes (sodium, potassium, chloride), bicarbonate, and creatine phosphokinase. Urinalysis will include specific gravity, pH, glucose, ketones, blood, protein, nitrate, leukocyte esterase, urobilinogen and bilirubin. If any parameter on the dipstick is abnormal, a urine sample should be sent to the central laboratory for quantitative measurement. If positive for protein and/or red blood cells, microscopic analysis will be performed by the central laboratory. Cotinine will be tested using the urine sample collected.
- m* Clinical laboratory testing at Screening Visit 1 will include hepatitis screen covering hepatitis B surface antigen (HBs Ag), hepatitis B surface antibody (HBs Ab), hepatitis B core antibody (HBc Ab), hepatitis C virus antibodies (HCV Ab), Human Immunodeficiency Virus (HIV) screen (Anti-HIV-1 and HIV-2 antibodies) and anti-nuclear antibody (ANA). In case of results showing HBs Ag (negative), and HBc Ab (positive), an HBV DNA testing may be performed prior to randomization to rule out a false positivity if the Investigator believes the patient is a false positive, or to clarify the serological status if the Investigator finds it unclear to interpret in absence of known HBV infection. In case of results showing HCV Ab (positive), an HCV RNA testing may be performed to rule out a false positivity, if the Investigator believes the patient is a false positive. Note: Anti-ds DNA antibody will be tested if ANA is positive ($\geq 1:160$ titer).
- n* Only for women of childbearing potential: serum pregnancy test at Screening/V1 and urine pregnancy tests at every 4 weeks from Randomization through EOT and at EOS. A negative result must be obtained at V1 and at V2 prior to randomization. In case of positive urinary test the study treatment will be withheld and a serum pregnancy test to confirm the pregnancy should be performed as soon as possible. Pregnancy will lead to definitive treatment discontinuation in all cases.
- o* Refer to central lab manual for collection details.
- p* If ADA assessment at week 12 is positive, additional measurements may be performed from PK samples collected at Week 4.
- q* The complete hematology panel will be performed.
- r* FeNO: measurement at sites only with access to FeNO equipment.
- s* Optional sputum sample at V2 should be collected post-randomization and prior to dosing with IMP, as long as patient consents to the optional collection. Only available at select sites in some countries.
- t* Archived samples may be used for research purposes related to COPD or other respiratory diseases such as asthma or inflammatory diseases (eg, exploratory biomarkers of disease or drug effect), pathway biology, additional drug safety assessments or development and validation of bioassay methods beyond those defined in the present protocol.
- u* Spirometry will be done locally according to European Respiratory Society (ERS)/American Thoracic Society (ATS) 2005 guidance but measured by a central laboratory. Spirometry will be performed during a trough period of bronchodilators according to their action duration, for example, withholding the last dose of salbutamol/albuterol or levosalbutamol/levalbuterol for at least 6 hours, withholding the last dose of ipratropium for at least 8 hours, withholding the last dose of LABA for at least 12 hours (ultra-long acting LABA like vilanterol should be withheld for at least 24 hours) and withholding the last dose of LAMA for at least 24 hours. This will be verified before performing the measurements. Note: When both pre and post-bronchodilator spirometry is assessed, the post-bronchodilator spirometry should be performed consistent with the mechanism of action of reliever (ie, 30 minutes for albuterol or other SABA).
- v* Following randomization and during the treatment period - if spirometry is not performed at the scheduled visit it should be performed at the following visit during the treatment period.
- w* The EXACT, SGRQ and EQ-5D-5L are to be completed in the patient's electronic diary.

- d* Electronic Diary will be used on daily basis for period of 12 weeks after ETD. The CAT assessment, and reliever medication will not be collected in patients after early treatment discontinuation.
- e* Complete physical examinations will include skin, nasal cavities, eyes, ears, respiratory, cardiovascular, gastrointestinal, neurological, lymphatic, and musculoskeletal systems.
- f* Vital signs, including systolic and diastolic blood pressure (mmHg), pulse rate (beats per minute), body temperature (°C), and respiratory rate will be measured at on-site visits. Body weight (kg) will be measured at EOT/EOS visits.
- g* ECG to be centrally collected & read.
- h* Hematology will include hemoglobin, hematocrit, platelet count, total white blood cell count with 5-part differential count, and total red blood cell count. Serum chemistry will include creatinine, blood urea nitrogen, glucose, lactate dehydrogenase, uric acid, total cholesterol, total protein, albumin, total bilirubin, alanine aminotransferase, aspartate aminotransferase, alkaline phosphatase, electrolytes (sodium, potassium, chloride), bicarbonate, and creatinine phosphokinase. Urinalysis will include specific gravity, pH, glucose, ketones, blood, protein, nitrate, leukocyte esterase, urobilinogen and bilirubin. If any parameter on the dipstick is abnormal, a urine sample should be sent to the central laboratory for quantitative measurement. If positive for protein and/or red blood cells, microscopic analysis will be performed by the central laboratory. Cotinine will be tested using the urine sample collected.
- i* Only for women of childbearing potential: urine pregnancy test at ETD and every 4 weeks through EOT and at EOS. In case of positive urinary test the study treatment will be withheld and a serum pregnancy test to confirm the pregnancy should be performed as soon as possible.
- j* Refer to central lab manual for collection details.
- k* If ADA assessment at week 12 is positive, additional measurements may be performed from PK samples from Week 4.
- l* FeNO: measurement at sites only with access to FeNO equipment.
- m* Optional sputum sample at ETD should be collected post-randomization and prior to dosing with IMP, as long as patient consents to the optional collection. Only available at select sites in some countries.
- n* Archived samples may be used for research purposes related to COPD or other respiratory diseases such as asthma or inflammatory diseases (eg, exploratory biomarkers of disease or drug effect), pathway biology, additional drug safety assessments or development and validation of bioassay methods beyond those defined in the present protocol.
- o* Spirometry will be done locally according to European Respiratory Society (ERS)/American Thoracic Society (ATS) 2005 guidance but measured by a central laboratory. Spirometry will be performed during a trough period of bronchodilators according to their action duration, for example, withholding the last dose of salbutamol/albuterol or levosalbutamol/levalbuterol for at least 6 hours, withholding the last dose of ipratropium for at least 8 hours, withholding the last dose of LABA for at least 12 hours (ultra-long acting LABA like vilanterol should be withheld for at least 24 hours) and withholding the last dose of LAMA for at least 24 hours. This will be verified before performing the measurements. Note: When both pre and post-bronchodilator spirometry is assessed, the post-bronchodilator spirometry should be performed consistent with the mechanism of action of reliever (ie, 30 minutes for albuterol or other SABA).
- p* Following randomization and during the treatment period - if spirometry is not performed at the scheduled visit it should be performed at the following visit during the treatment period.
- q* The EXACT, SGRQ and EQ-5D-5L are to be completed in the patient's electronic diary.

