Multinational, randomized, double-blind, placebo controlled, parallel group (2 groups), Proof of Concept (PoC) study that is designed to assess the efficacy, safety, and tolerability of SAR440340 in patients with moderate-to-severe COPD on an established Long-acting β 2 adrenergic agonist (LABA), Long-acting muscarinic antagonist (LAMA), and/or ICS background therapy (double or triple therapy). Patients will be treated with SAR440340 or placebo for a minimum of 24 weeks and up to a maximum of 52 weeks*, and a 20-week safety follow-up period.

** This study employs a variable treatment duration from 24 to 52 weeks to maximize data for the primary endpoint (annualized rate of exacerbation) in a time-efficient manner. Patients enrolled in the trial will remain in the treatment period for up to a maximum of 52 weeks or until the last patient randomized completes a minimum treatment period of 24 weeks. Of note, the accrual and drop-out rates will be closely monitored. If the accrual rates are significantly lower than planned and/or the drop-out rates are higher than expected, the minimum treatment duration may be extended to achieve the desired amount of total exposure. The maximum treatment duration of 52 weeks will not be changed.*

The study duration is outlined below:

- Screening period (10 days to 4 weeks)
- Randomized investigational medicinal product (IMP) treatment period (24 to 52 weeks)
- Post IMP safety follow-up treatment period (20 weeks).

At screening, patients must be on standard of care background therapy, for 3 months prior to Visit 2/Randomization and at a stable dose for at least 1 month prior to the Screening Visit 1, including either:

- Double therapy: LABA + LAMA or ICS + LABA or ICS + LAMA.

OR

- Triple therapy: ICS + LABA + LAMA.

Patients who satisfy the inclusion and exclusion criteria will be randomized (1:1) to:

- SAR440340 (300 mg) administered as 2 SC injections every 2 weeks (q2w) for 24 to 52 weeks
- Matching placebo for SAR440340 administered as 2 SC injections q2w for 24 to 52 weeks

It is planned to enroll approximately 50% of patients on ICS-containing background therapy (ICS+LABA; ICS+LAMA or ICS +LABA+LAMA).

Patients must be willing to stay on their established background medication for COPD throughout the duration of the study.

Visits up to 52-week IMP treatment period will occur every other week and will be followed by a 20-week observational follow-up period.

Treatment discontinuation follow-up:

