2.5.4 Windows for time points

Visit windows based on days relative to the first IMP administration will be used to map the efficacy parameters (Table 6), selected safety variables (Table 7) and PK/PD variables (Table 8) to each scheduled visit. Date of randomization will be used as the reference date for patients not treated. The following rules will be applied:

1. For efficacy parameters, only scheduled measurements will be considered. If a patient has more than one measurement for the same parameter at different dates within the same visit window, the one that is closest to the target date will be used (or the latest in case of tie).
2. Only values from the central laboratory will be considered for laboratory variables.
3. For the same laboratory/vital sign/ECG/PK/PD parameter, if a patient has more than one measurement at different dates within the same visit window, the measurement that is closest to the target date will be used (or the latest in case of tie).
4. When a patient has more than one measurement on the same laboratory/vital sign/ECG/PK/PD parameter on the same date, then the one with the later/largest sample ID will be used.
5. For procedures planned on Visit 2, if it is done on the same date as the first IMP but the performance time is missing, it will be assigned to the Visit 2 time window.

Table 6 – Time window for efficacy endpoints

Visit	Target Day	Pre-BD spirometry	Post-BD spirometry
Visit 1 (Wk-4 to Wk-1)	-28±3	-28±3	-28±3
Visit 2 (Week 0)	1	≤1	≤1
Visit 3 (Week 2)	15	2-21	2-21
Visit 4 (Week 4)	29	22-42	22-42
Visit 6 (Week 8)	57	43-70	43-70
Visit 8 (Week 12)	85	71-98	71-126
Visit 10 (Week 16)	113	99-126	
Visit 12 (Week 20)	141	127-154	
Visit 14 (Week 24)	169	155-182	127-266
Visit 16 (Week 28)	197	183-210	
Visit 18 (Week 32)	225	211-238	
Visit 20 (Week 36)	253	239-266	
Visit 22 (Week 40)	281	267-294	
Visit 24 (Week 44)	309	295-322	
Visit 26 (Week 48)	337	323-343	
Visit 27 (Week 50)	351	344-357	
EOT (Week 52)	365	358-392	267-392
F1 (Week 60)	421	393-462	393-462
EOS (Week 72)	505	≥463	≥463

Table 7 – Time window for safety endpoints

Visit	Target Day	Vital signs	ECG	Hematology, biochemistry, urinalysis	Heptitis and HIV serology tests, quantiferon gold testing, serum pregnancy test	Urine pregnancy test
Visit 1 (Week -4 - 0)	-28±3	< -7	<-7	<-7	≤1	
Visit 2 (Week 0)	1	-7-1	-7-1	-7-1		≤1
Visit 3 (Week 2)	15	2-21				
Visit 4 (Week 4)	29	22-35				2-42
Visit 5 (Week 6)	43	36-49				
Visit 6 (Week 8)	57	50-63		2-84		43-70

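### On the nominal schedule, a make-up pre-bronchodilator spirometry for Weeks 4 to 44 falls on the first day of the next SAP window, where it is dropped or relabelled, and no SAP rule maps it back

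*Protocol*

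**What the plan says.** Protocol 1.3.1, footnote v, provides for recovery of a missed test: "if spirometry is not performed at the scheduled visit it should be performed at the following visit during the treatment period". Protocol 1.3.2, footnote p, repeats this for patients who have stopped treatment early.

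The following visit is two weeks later: "Visits up to 52-week IMP treatment period will occur every other week". On timing: "The visit schedule should be adhered to within ±3 days for the screening period and randomized IMP treatment period". After early discontinuation the allowance is ±5 days, and odd-numbered visits may be held by phone (Protocol 4.1).

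SAP 2.5.4 assigns each measurement to a visit by day windows. Its first rule is: "For efficacy parameters, only scheduled measurements will be considered". If two values fall in one window, "the one that is closest to the target date will be used (or the latest in case of tie"). The rows of Table 6 behind the key secondary endpoint give target day and pre-bronchodilator window:

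- "Visit 10 (Week 16) 113 99-126"
- "Visit 12 (Week 20) 141 127-154"
- "Visit 14 (Week 24) 169 155-182 127-266" (the last range is the post-bronchodilator window)

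SAP 2.4.4.2.1 averages Weeks 16, 20 and 24 in a repeated-measures model and does not impute missing FEV1 in the main analysis.

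**The concern.** The protocol rule exists so that a missed spirometry is not lost. It sends the test to an odd-numbered visit, midway between two four-weekly spirometry visits. Table 6 divides the calendar at that midpoint and gives the midpoint day to the later visit. The two rules therefore do not work together. A patient may go through a further bronchodilator washout and test for a value that does not fill the gap it was meant to fill.

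At stake is the completeness of the FEV1 series behind the key secondary endpoint. There is also a reproducibility question. Because the SAP does not say whether a make-up test is scheduled, two programmers could both follow it and build different datasets.

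**Working it through.** **1. The plan's own figure.** The only stated power that the windows could touch is 92.6% for FEV1 (Protocol 9.2, which labels it post-bronchodilator; SAP 1.3 uses the same inputs for pre-bronchodilator and states above 90%). Inputs: difference 0.12 L, SD 0.3 L, two-sided 5%, 170 per group, 15% missing.

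- n = 170 × 0.85 = 144.5 per group
- SE = 0.3 × √(2/144.5) = 0.0353 L
- power ≈ Φ(0.12/0.0353 − 1.96) = Φ(1.44) = 92.5% (92.3% by noncentral t)
- least significant difference = 0.069 L, against 0.07 L stated

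The figure reproduces.

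**2. Where a make-up test lands.** Make-up day = target + 14. SAP Table 7 confirms the target days of Visits 11, 13 and 15.

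| Missed test | Target | Pre-bronchodilator window | Following visit | Nominal make-up day | Window it falls in |
|---|---|---|---|---|---|
| Week 16 | 113 | 99-126 | Visit 11 | 127 | Week 20 (127-154) |
| Week 20 | 141 | 127-154 | Visit 13 | 155 | Week 24 (155-182) |
| Week 24 | 169 | 155-182 | Visit 15 | 183 | Week 28 (183-210) |

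The same one-day miss occurs at Weeks 4, 8, 12, 28, 32, 36, 40 and 44. Weeks 2, 48 and 50 differ: their windows end 8 days before the following visit, and that visit has its own row in Table 6.

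**3. With the visit allowance.** At ±3 days, a make-up falls 11 to 17 days after target. Days +11 to +13 (for Week 16, Days 124-126) stay in the right window: 3 of 7. Days +14 to +17 (Days 127-130) go to the next: 4 of 7, or 57% if days are equally likely. If visits cluster on the nominal day, the share is (1 + p0)/2, where p0 is the probability of the exact day. A normal spread over whole days, truncated at ±3, with an assumed SD of 2, 1.5 or 1 day, gives 61%, 64% or 70%. At ±5 days, days +14 to +19 are misplaced: 6 of 11.

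**4. What then happens.** In the later window, a ±3-day make-up is 28 − 17 = 11 to 28 − 14 = 14 days from that target. The visit's own test is at most 3 days away, so it always wins. If that test is absent, the make-up is kept under the later label. A Week 16 or Week 20 make-up then remains inside the Week 16-24 average, one visit late. A Week 24 make-up becomes Week 28 and leaves it.

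**5. Size.** The documents give no rate of missed tests. If an assumed 0%, 2%, 5% or 10% of otherwise available values were lost, the calculation in step 1 gives 92.5%, 92.0%, 91.2% or 89.7%. It treats the endpoint as a single time point, whereas the planned model also uses the patient's other visits.

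**The case against.** The strongest reply is that Table 6 follows an ordinary convention. Day 127 is exactly 14 days from both Day 113 and Day 141, so calling it Week 20 is no less accurate than calling it Week 16. Holding Day 130 in Week 16 keeps a value 17 days from one target and 11 from the other. This is fair as far as calendar distance goes. It does not answer the point that the protocol orders the test to replace a particular visit and the SAP has no rule that lets it do so.

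The other side is also right to limit the point. A reader might infer any of the following, and the documents do not support them:

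- **That every window fails, or every make-up test is lost.** Weeks 2, 48 and 50 are different, 3 of 7 permitted days map correctly, and a misplaced value is dropped only if the next test was done.
- **That the first rule in SAP 2.5.4 excludes make-up tests.** A test that the protocol directs can equally be read as scheduled. The text is silent, not exclusionary.
- **That clinically important deterioration is harmed.** It uses trough FEV1, but the SAP does not say that its events must come from the one value chosen per window.
- **That post-bronchodilator FEV1 is affected at Week 24.** That window, 127-266, holds Day 183.

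A patient whose planned treatment ends at Week 24 has no later treatment visit, so no Week 24 make-up arises. Under the planned accrual, with 335 of 340 enrolled before the last month, such patients should be few.

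**Conclusion.** The protocol's recovery rule and the SAP's visit mapping do not fit together for pre-bronchodilator spirometry at Weeks 4 to 44. The mismatch follows from the stated days alone: one day on the nominal schedule, and 4 of 7 permitted days with the ±3-day allowance. The consequence depends on the next test: the make-up is dropped if that test is done and relabelled if it is not.

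The practical effect is probably small. It scales with a number of make-up tests that the documents do not give, and even an assumed 10% loss of values leaves power near 90%. Nothing here shows bias between the arms, and the primary endpoint is not involved. This is a cheap improvement that uses data already collected. It is not a threat to the key secondary result.

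**What to change.** Reconcile footnotes v and p of the protocol schedules with SAP 2.5.4 before database lock.

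1. In the first rule, state that a make-up test under footnote v or p counts as a scheduled measurement for the visit that was missed.
2. For Weeks 4 to 44 only, move the pre-bronchodilator windows so that they hold the following visit. One workable set joins the Table 7 vital-sign windows of the scheduled and following visits, which is target −7 to target +20: Week 4 22-49, Week 8 50-77, Week 12 78-105, Week 16 106-133, Week 20 134-161, Week 24 162-189, Week 28 190-217, Week 32 218-245, Week 36 246-273, Week 40 274-301, Week 44 302-329. Week 48 then starts at Day 330. Leave its upper limit and the Week 2, Week 50 and EOT rows unchanged.

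On-time tests stay where they are, at ±3 days or at ±5 after discontinuation. All permitted make-up days (+11 to +17, or +9 to +19) map to the missed visit.

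The cost is SAP wording and window programming, with no new procedure. A make-up value may lie up to 19 days after target. The gain is smaller after early discontinuation, because a phone visit yields no spirometry. One side effect needs a line in the SAP: if a planned EOT falls on an odd-numbered visit, its test also moves to the earlier window (Day 183 from Week 28 to Week 24), where an on-time Week 24 test would displace it.
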